## **5. SUBJECT DISPOSITION**

The number of subjects included in each subject set (i.e. enrolled, safety and PK) will be summarized.

The number and percentage of subjects who completed and discontinued the study will be presented for the enrolled set. Reasons for discontinuation as recorded on the termination page of the electronic case report form (eCRF) will be summarized (number and percentage) for the enrolled set. All enrolled subjects who discontinued from the study will be listed and the reason for discontinuation will be provided. The subjects who completed the study will be those who completed the final scheduled visit on Day 9 of Week 4 for the rich PK sample subset or on Day 8 of Week 4 for the sparse PK sample subset.

Subject disposition and study analysis sets will be listed for the enrolled set.

## **6. PROTOCOL DEVIATIONS**

All protocol deviations and violations will be recorded by the site separately from the clinical database. The CRO/Shire will classify the protocol deviations and violations per the agreed protocol study deviation tools. The Shire study team will review the protocol deviations and their classification throughout the study and before the database lock.

Decisions of the review will include accuracy of protocol deviations and violations categorization.

For any criteria for protocol deviations that can be completely implemented by a computer program, the detailed algorithm will be agreed upon. Details of such algorithms will be included in the derived dataset specifications and finalized before the database lock.

Confirmed protocol violations and protocol deviations will be documented in the Protocol Violation/Deviation tracker for the study. Protocol deviations/violations will be summarized by category and site, for the safety set. Protocol deviations/violations will be listed for the enrolled set.

## 7. DEMOGRAPHIC AND OTHER BASELINE CHARACTERISTICS

### 7.1 Demographic and other Baseline Characteristics

Descriptive summaries of demographic and other baseline characteristics will be presented for the safety set and PK set.

The following demographic characteristics will be summarized in the following order in the tables: age, sex, ethnicity, race, weight, height, and body mass index (BMI). In addition, other baseline characteristics such as years since diagnosis of ADHD, ADHD Subtype, baseline ADHD-RS-5 (Child, Home Version) total score, and baseline Clinical Global Impressions - Severity of Illness (CGI-S) score will be summarized.

The ADHD-RS-5, which measures the behavior of children, is an 18-item questionnaire that requires the respondent to rate the frequency of occurrence of ADHD symptoms as defined by Diagnostic and Statistical Manual of Mental Disorders (DSM-5) criteria. Each item is scored on a 4-point scale ranging from 0 (reflecting no symptoms) to 3 (reflecting severe symptoms) with total scores ranging from 0 to 54. The ADHD-RS-5 total score will be calculated as the sum of the individual items from the ADHD-RS-5.

The CGI-S is performed to rate the severity of a subject's condition on a 7-point scale ranging from 1 (normal, not at all ill) to 7 (among the most extremely ill subjects).

Continuous variables, such as age, weight, height, BMI, years since diagnosis of ADHD, and baseline ADHD-RS-5 total score will be summarized using descriptive statistics including number of subjects (n), mean, standard deviation (SD), median, minimum, and maximum. Categorical variables such as sex, ethnicity, race, ADHD Subtype, and baseline CGI-S score will be summarized by reporting the number and percentage of subjects in each category. All summarized values will be taken from the Screening Visit or Predose assessments (for baseline weight and BMI).

Age will be calculated as the difference between date of birth (DOB) and date of informed consent (DINFC), truncated to years, using the following formula:

Age = floor((intck('month',DOB,DINFC) - (day(DINFC) < day(DOB))) / 12)

For PK analyses age will also be calculated without truncation as the difference between DOB and DINFC.

Height and weight will be summarized in international system of units.

Height and weight at predose assessment will be used to calculate BMI using the formula below:

BMI = Weight in kilograms / (Height in meters)

Number of years since diagnosis of ADHD will be based on DINFC.

Demographics and baseline characteristics will be listed for the safety set.

## **7.2 Medical History**

At the Screening Visit demographic information, a complete medical and medication history will be collected including recent ingestion of medication (30 days prior to entering the screening period) and history of respiratory, cardiovascular, renal, gastrointestinal, hepatic, endocrine, hematological, neurological, psychiatric, and other diseases.

Medical history will be listed for the safety set.

The Mini International Neuropsychiatric Interview for Children and Adolescents (MINI-KID) version 7.0.2 collected at the Screening Visit will be listed for the safety set.

ADHD non-medication treatment history, behavioral therapy history, collected at the Screening Visit (Visit 1) will be listed for the safety set.

For ADHD medication history collected at the Screening Visit (Visit 1), version September 1, 2017 of the World Health Organization (WHO) drug dictionary will be used to classify ADHD medications by preferred term. ADHD medication history will be summarized separately by the number and percentage of subjects receiving each medication within each preferred term for the Safety Set. ADHD medication history will be listed for the safety set.

## 8. EXTENT OF EXPOSURE AND TREATMENT COMPLIANCE

### 8.1 Exposure to Investigational product

A listing will be created by subject number and will show the date and time of dose administration and investigational product accountability for the safety set.

Exposure to SHP465 6.25 mg will be summarized for the safety set.

For the investigational product SHP465 all dosing information (total dose, average daily dose and cumulative dose) will be listed and the following statistics will be calculated by study visit:

- Days of dosing: number of days on which dose information was available and non-zero
- Total dose (mg): total number of capsules taken  $\times$  dose level (6.25 mg)
- Average daily dose (mg/day): the total dose / total days of dosing
- Cumulative dose (mg): sum of total dose since start of treatment
- Duration of exposure in weeks: the total days of dosing / 7

A statistical summary will be applied to present for each of the above statistical quantities.

Subjects will be categorized in 1 week increments by their overall duration of exposure in days and will be presented using subject counts and percentages.

In addition, person-time (overall total exposure in days) will be derived for SHP465 6.25mg. It is calculated as total number of days in which SHP465 6.25mg was taken for each subject (total days of dosing for the treatment period), and then sum over all subjects for the treatment period.

If a subject is lost to follow up without returning the leftover of investigational product and without providing subsequent safety information, then the subject's dose information will be treated as missing. In particular, for subjects who are lost in the follow up after the Baseline Visit (predose on Day 1), it will not be assumed that any of the investigational product has been ingested unless there is a post-baseline safety assessment. Subjects who do not return the investigational product but return to the site for the following visit will have the dose return information entered into the database on the scheduled visit.

## 8.2 Measurement of Treatment Compliance

Treatment compliance will be calculated as follows:

For whole capsules:

$$\text{Compliance} = \frac{\text{Total Capsules Taken} \times 100}{\text{Capsules Prescribed per Protocol}}$$

For capsule contents sprinkled in applesauce:

$$\text{Compliance} = \frac{\text{Total Sprinkled Doses Taken} \times 100}{\text{Capsules Prescribed per Protocol}}$$

Where,

- if the subject completed the treatment period: capsules prescribed per protocol = 28;
- if the subject discontinued early in the treatment period, capsules prescribed per protocol = date of treatment discontinuation – date of first dose +1.

Descriptive statistics for investigational product compliance will be presented for the safety set. Individual subject treatment compliance will be listed by category. The investigation product treatment compliance will be categorized as <80%, 80-120%, or >120%. The category 80-120% will be considered compliant for analysis purpose.

## **9. PRIOR AND CONCOMITANT MEDICATIONS/TREATMENTS**

The WHO Drug Dictionary version September 1, 2017 will be used to classify prior and concomitant medications by preferred drug name.

Prior medication or treatment is defined as any medication (including but not limited to herbal treatments, vitamins, nonpharmacological treatment, such as behavioral treatment) received within 30 days (or PK equivalent of 5 half-lives, whichever is longer) prior to the date of the administration of investigational product.

Concomitant medication or treatment is defined as any medication or treatment with a start date prior to the date of the first dose of investigational product and continuing after the first dose of investigational product or with a start date between the dates of the first dose and last dose of investigational product, inclusive.

Any medication with a start date after the date of the last dose of investigational product (post-treatment) will not be considered a concomitant medication.

Both prior and concomitant medication usage will be summarized separately by the number and percentage of subjects receiving each medication within each preferred term for the safety set. Medications can be counted both as prior and concomitant medication. For the purpose of summaries multiple medication usage by a subject in the same category will be counted only once.

All prior, concomitant and post-treatment medications/treatments will be listed for the safety set.

**10. EFFICACY ANALYSES**

Not applicable.

## 11. SAFETY ANALYSES

The safety analysis will be performed using the safety set. Safety endpoints include the occurrence of treatment-emergent AEs (TEAEs), vital signs (systolic and diastolic blood pressure, pulse rate, respiratory rate, and body temperature), weight, height, electrocardiogram (ECG) results, the Columbia-Suicide Severity Rating Scale (C-SSRS), clinical laboratory tests (biochemistry, hematology, and urinalysis), the parent/ legally authorized representative (LAR)-completed Children's Sleep Habits Questionnaire (CSHQ) and the Post Sleep Questionnaire (PSQ).

For each safety endpoint, unless otherwise specified, the last value collected before the first dose of the administration of investigational product will be used as baseline for all analyses of that safety endpoint.

Except for AE data, only baseline assessments from baseline visit (predose on Day 1 of Week 1) and post-baseline assessment up to the final scheduled visit (Day 9 of Week 4 for rich PK sample subset or Day 8 of Week 4 for sparse PK sample subset) that were collected on or before 2 days after the last dose of the investigational product will be analyzed.

A Final on-Treatment Assessment (FoTA) will be defined as the last valid assessment obtained after baseline and whilst on investigational product (on or before 2 days after the last dose date).

### 11.1 Adverse Events

Adverse events will be coded using Version 20.1 of the Medical Dictionary for Regulatory Activities (MedDRA).

Treatment-emergent AEs are defined as AEs that started or deteriorated on or after the date of the first dose of investigational product, and no later than 3 days following the last dose of investigational product. If more than 1 AE with the same preferred term is reported before the date of the first dose of the investigational product, then the AE with the greatest severity will be used as the benchmark for comparison to the AEs occurring during the treatment period under the preferred term.

An overall summary of the number of subjects with TEAEs will be presented, including the number and percentage of subjects with any TEAEs, serious TEAEs, TEAEs related to investigational product, TEAEs leading to discontinuation from the study, and TEAEs leading to death.

The number and percentage of subjects reporting TEAEs will be tabulated by system organ class (SOC) and preferred term (PT); by SOC, PT, and maximum severity. TEAEs considered related to investigational product will also be summarized by SOC and PT. If more than 1 AE occurs with the same PT for the same subject, then the subject will be counted only once for that PT using the most severe and most related occurrence for the summarization by severity and by relationship to investigational product.

For subjects on SHP465 the incidence of all TEAEs will be summarized by preferred term, and sorted by decreasing frequency. Serious TEAEs, TEAEs related to investigational product, and TEAEs leading to discontinuation from the study will be summarized by SOC and PT for the safety set. Listings will be presented for all AEs, serious TEAEs, TEAEs related to investigational product, and TEAEs leading to discontinuation from the study.

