8 ADVERSE AND SERIOUS ADVERSE EVENTS ASSESSMENT

8.1 Definition of Adverse Events, Period of Observation, and Recording of Adverse Events

An AE is any untoward medical occurrence in a clinical investigation subject administered a pharmaceutical product and that does not necessarily have a causal relationship with this treatment. An AE can therefore be any symptom, unfavorable and unintended sign (including an abnormal laboratory finding), or disease temporally associated with the use of a medicinal (investigational) product, whether or not related to the medicinal (investigational) product (ICH Guideline E2A [1994]).

All AEs are collected from the time the informed consent form is signed until the defined follow-up period stated in Section 7.1.3. This includes events occurring during the screening phase of the study, regardless of whether or not investigational product is administered. Where possible, a diagnosis rather than a list of symptoms and signs should be recorded. If a diagnosis has not been made, then each symptom and sign should be listed individually. All AEs should be captured in the source documents. In addition to untoward AEs, unexpected benefits outside the investigational product indication should also be captured.

All AEs must be followed to closure (the subject's health has returned to his/her baseline status or all variables have returned to normal), regardless of whether the subject is still participating in the study. Closure indicates that an outcome is reached, stabilization achieved (the investigator does not expect any further improvement or worsening of the event), or the event is otherwise explained. When appropriate, medical tests and examinations are performed so that resolution of event(s) can be documented.

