8.1.1 Severity Categorization

The severity of AEs must be recorded during the course of the event including the start and stop dates for each change in severity. An event that changes in severity should be captured as a new event. Worsening of pretreatment events, after initiation of investigational product, must be recorded as new AEs (for example, if a subject experiences mild intermittent dyspepsia prior to dosing of investigational product, but the dyspepsia becomes severe and more frequent after the dose of investigational product has been administered, a new AE of severe dyspepsia [with the appropriate date of onset] is recorded in the source document).

The medical assessment of severity is determined by using the following definitions:

Mild: A type of AE that is usually transient and may require only minimal treatment or therapeutic intervention. The event does not generally interfere with usual activities of daily living.

Moderate: A type of AE that is usually alleviated with specific therapeutic intervention. The event interferes with usual activities of daily living, causing discomfort but poses no significant or permanent risk of harm to the research subject.

Severe: A type of AE that interrupts usual activities of daily living, or significantly affects clinical status, or may require intensive therapeutic intervention.

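### Read literally, the SAP's TEAE rule counts a pre-dose event that becomes milder on drug as treatment-emergent, because the protocol records every change in severity as a new event

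*SAP*

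**What the plan says.** **How events are recorded.** Protocol 8.1 collects AEs from consent: "This includes events occurring during the screening phase of the study, regardless of whether or not investigational product is administered". Screening may last up to 32 days. Protocol 8.1.1 requires severity to be recorded "including the start and stop dates for each change in severity", and adds: "An event that changes in severity should be captured as a new event". It then states separately: "Worsening of pretreatment events, after initiation of investigational product, must be recorded as new AEs". Improvement is not exempted from the general sentence.

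**How events are classified.** SAP 11.1 says: "Treatment-emergent AEs are defined as AEs that started or deteriorated on or after the date of the first dose of investigational product". The window closes 3 days after the last dose. The next sentence opens "If more than 1 AE with the same preferred term is reported before the date of the first dose of the investigational product" and continues "then the AE with the greatest severity will be used as the benchmark for comparison to the AEs occurring during the treatment period".

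**What else bears on it.** SAP 11.1.1 merges overlapping or adjacent TEAEs, but only to compute duration, and only for insomnia, weight decrease and decreased appetite. SAP 17 amends the protocol's TEAE definition only by moving the end of the window from the first dose to the last dose.

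**The concern.** The two documents use *event* differently. In the protocol's recording rule, one clinical episode becomes several AE records, each with its own start date. The SAP's definition treats a start date on or after first dose as sufficient. A post-dose start date can therefore mean only that an existing complaint eased.

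TEAEs are a core safety output of a single-arm study whose primary objective includes safety and tolerability. For the three events tabulated in SAP 11.1.1, the error would reach the number of subjects, the number of TEAEs, the onset day, the severity counts and the weekly incidence. The study has no control arm against which such artefacts would balance out.

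**Working it through.** The plan states no figure on this point, so there is none to reproduce. The check applies the rules to records, then sizes one misclassification.

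**One child, literal reading (illustrative).** Moderate insomnia starts on Day -6, is ongoing at first dose on Day 1, and becomes mild on Day 3.

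1. Protocol 8.1.1 closes the moderate record and opens a mild record starting on Day 3.
2. Under SAP 11.1, Day 3 is after first dose, so the mild record *started* in the window and is a TEAE.
3. The benchmark sentence requires more than one pre-dose AE of the term. This child has one, so as worded it is not triggered.
4. SAP 11.1.1 onset day = (onset date - first-dose date) + 1, which gives Day 3. The complaint actually began before dosing.
5. The SAP 11.1.1 merge joins TEAEs only. The pre-dose record is not a TEAE, so it is not joined, and the computed duration also starts on Day 3.

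**All severity combinations.** Take pre-dose severity (mild, moderate, severe) by on-treatment severity. The record is either a continuing event whose severity changed or a new onset after the pre-dose event resolved. The table gives the number classified as TEAEs under two readings: the *started* limb alone, and the benchmark used as a filter (a TEAE only if more severe than before dosing).

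| On-treatment record | Cases | Started limb alone | Benchmark as filter | Sensible target |
|---|---|---|---|---|
| Continuing event, milder | 3 | 3 | 0 | 0 |
| Continuing event, worse | 3 | 3 | 3 | 3 |
| New onset after resolution, milder | 3 | 3 | 0 | to be stated |
| New onset after resolution, same severity | 3 | 3 | 0 | to be stated |
| New onset after resolution, more severe | 3 | 3 | 3 | 3 |

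The *started* limb alone misclassifies all 3 improving continuing events. The filter removes that error, but it also leaves out 6 of 9 new onsets after resolution. SAP 11.1 does not say which reading governs.

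**The trigger depends on record splitting.** A child whose single episode changed severity before dosing has two pre-dose records under Protocol 8.1.1 and can meet the more-than-one condition. A child with the same unbroken episode at constant severity cannot. The same clinical course on drug could then be classified differently.

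**Size.** SAP 2.5 expects about 24 enrolled, with 20 planned completers. One misclassified child moves a preferred-term incidence by 1/24 = 4.2 percentage points, or 1/20 = 5.0 with 20 children. This holds only if the child has no other TEAE of that term, because SAP 11.1 counts each subject once per preferred term. The number of TEAEs rises by one for each such record regardless.

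**The case against.** The best reply is that the benchmark sentence is a tie-break. It names the record to use when there are several pre-dose AEs, and takes for granted that a single pre-dose AE is compared too. On that reading mild after moderate is not a deterioration, the improving event is excluded, and the word *deteriorated* has a purpose. SAP 18.8 supports this: it imputes mild for a pre-dose AE with missing severity, which makes sense if pre-dose severities are compared with later ones. In addition, Protocol 8.1.1's only example of a pretreatment event carried into treatment is one that worsens.

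This is a plausible account of the intent, and it is why the point is limited to the literal reading. It does not settle the text. Under the definition, starting is enough without deteriorating, the condition says more than one, and the consequence of the comparison is not stated.

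It is also fair that the summaries are descriptive, that all AEs are listed, that affected children can be traced among about 24, and that the literal reading over-counts, which is the cautious direction for incidence. Listings do not correct the summary tables, however, and a false onset day is not cautious in either direction.

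A reader might infer more: that the plan both creates false TEAEs and loses true recurrences. The documents do not support this as a settled result. For a child with one pre-dose AE the two outcomes come from competing readings. Both could arise in one dataset if the filter were applied only to children with several pre-dose AEs, but the SAP does not say so. Comparing later events with the worst pre-dose severity is in any case a defensible convention. Nor do the documents give a rate of pre-dose AEs or recurrences from which to estimate a share of events lost.

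**Conclusion.** The point holds as a gap between the protocol's recording rule and the SAP's classification rule. Followed as written, the plan counts a single ongoing pre-dose event that becomes milder on drug as a TEAE, with a false onset day for the three SAP 11.1.1 events. The effect is confined to children with pre-dose AEs, at 4.2 percentage points per child on a preferred-term incidence under the conditions above. How many children would be affected cannot be derived from the documents. The conclusion assumes that sites follow Protocol 8.1.1 for improvements and that the programming follows the wording of SAP 11.1. It should be corrected before database lock, because it changes tabulated safety results and is more than a missing detail.

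**What to change.** In SAP 11.1:

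- State that a record starting on or after first dose which continues an event ongoing at first dose (same preferred term, overlapping or adjacent dates) is a TEAE only if its severity exceeds the pre-dose severity.
- Make the pre-dose severity comparison apply when there is one or more pre-dose AE of the term, and state its consequence. The existing choice of the greatest pre-dose severity can stand.
- State whether a new onset after a resolved pre-dose event counts whatever its severity. If it does, the rule gives 0 of 3 improving continuing events, 3 of 3 worsening ones and 9 of 9 new onsets as TEAEs.

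Use the same rule for the TEAE counts and onset day in SAP 11.1.1, and record the clarification in SAP 17. SAP 18.7 leaves incomplete AE stop dates unimputed, so the linking rule should also say how a record with such a date is treated.

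The cost is a few lines of text and a small programming change. No new data are needed, because Protocol 8.1.1 already collects the severity and dates of each change.
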